3.1. Test Accuracy Study Design

ENDCaP-C is a prospective diagnostic test accuracy study. An outline of the test accuracy study is shown in the study schema. It is designed to generate a comparison of measurements obtained by the index test with those obtained by reference standard. In this way the accuracy of the index test can be estimated. A reference standard is a test that confirms or refutes the presence or absence of disease beyond reasonable doubt. Therefore it is sometimes also known as the gold standard. The methylation test is the index test whereas the reference standard will be histology at 4-12 months after the methylation test.

In the study the results of the index test will first be compared with histology of biopsy samples taken at the first standard surveillance colonoscopy (labelled "diagnostic value of the test" in the study schema below) and then with the reference standard colonoscopy (labelled "prognostic value of the test" in the study schema). The second comparison is the primary comparison for the study as the reference standard colonoscopy used at this point will be of the highest quality possible, utilising dye spray to increase dysplasia detection and restricting to nominated, experienced colonoscopists at each site. In addition this colonoscopy will occur 4-12 months after the initial colonoscopy, which will increase the chances of finding dysplasia that was initially not detected (i.e. identifying patients with false negative initial histology).

In order to ensure efficiency in the study design, whilst all patients with positive tests for methylation will undergo the reference standard colonoscopy, only a sample of those with negative tests will be selected for reference standard colonoscopy. The rationale for this is given in the sample size section below.

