6.4. Late Reference Standard (see 3.6, Study Schema)

All histologically negative patients with positive methylation status (test positives) will be identified by the ENDCaP-C Study Office and will be invited to undergo early repeat colonoscopy. Twice as many histologically negative patients that have negative methylation status will be randomly selected without matching (test negatives) by the ENDCaP-C Study Office and also will be invited to undergo early repeat colonoscopy. The late reference standard colonoscopy will be undertaken 4-12 months after the standard colonoscopy, blinded to methylation status. This reference assessment will be standardised using dye spray and targeted biopsy to maximise dysplasia detection, and should be performed by nominated, experienced colonoscopists at each site.

During this procedure, biopsy samples will be taken. As with the standard colonoscopy at trial entry, our requirements are for two samples from the left side of the colon, two from the right side of the colon and one from the rectum. We do not object to additional biopsies being taken and sent to us if this is preferred at a site. Each biopsy will involve two "bites" from the mucosa using a spiked endoscopy forceps as is current standard practice.

Biopsy samples should be embedded in paraffin and processed and analysed as per local practice. It is important that biopsies from different sites (left, right and rectum) should not be embedded into the same block and so we expect a minimum of THREE blocks, one per site. If this is not possible or unavoidable, guidance on the how to identify the appropriate biopsies must be provided.

The ENDCaP-C Study Office will send out instructions on sample requirements to all participating centres.

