6.4.2 Blood sample collection

At the time of the late reference standard colonoscopy, an addition 10ml venous blood sample will be taken patients who have consented to sample collection. This will be used to test for Wnt antagonist methylation in serum.

The ENDCaP-C Study Office will send out instructions on sample requirements to all participating centres.

6.5. Avoidance of Study Biases:

The generalisability of the study will be assured by aiming to recruit a consecutive sample of patients attending for routine surveillance, who fall within the high risk category. Information will be collected on risk factors in all study patients and investigate whether the diagnostic value of methylation varies according to patient characteristics.

Misclassification bias can occur in test accuracy studies where the reference standard test is inaccurate. The initial colonoscopy will be a routine surveillance procedure, making the study a pragmatic one which assesses the incremental value of methylation over and above standard current practice. The reference standard colonoscopy will be of the highest quality possible, utilising dye spray to increase dysplasia detection and will be restricted to experienced, nominated colonoscopists at sites. In addition, this colonoscopy will occur 4-12 months after the initial colonoscopy, which will increase the chances of finding dysplasia that was initially not detected (i.e. identifying patients with false negative initial histology). Whilst there is a risk that new dysplasia may develop during this period, this time period has been chosen to minimise the risk. This should not introduce bias as it should be equal in both methylation test positives and negatives. Long term follow up of this cohort of patients will be undertaken, to assess late conversion rate to neoplasia. This will be undertaken outside of this study.

Reference standard colonoscopies will only be undertaken in a sample of methylation test negatives. As this sample will be chosen randomly without matching it should be representative of all test negatives, and the results not suspect to partial verification bias.

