It is acknowledged that verification bias cannot be completely eliminated due to the fact that the histologist will be aware that any repeat colonoscopy will consist of both test positives and test negatives. Hence to minimise this bias so that histologists cannot base their decision criteria for histological classification by knowledge of the allocation ratio, we will match the numbers of controls recruited at the study level and not within each hospital.

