6.6. Withdrawal of treatment or protocol violation

Patients may withdraw at any time during the study if they choose not to continue, or if their clinical team feel that continued participation in the study is inappropriate.

There are different types of withdrawal:

- The patient would like to withdraw from the study specific tests and procedures, but is willing to be
 followed-up according to the study protocol (i.e. has agreed to attend study specific follow-up visits
 and that follow-up data can be collected)
- The patient does not want to attend study specific follow-up visits, but has agreed to be followedup according to standard practice (i.e. has agreed that follow-up data can be collected at standard clinic visits)
- The patient is not willing to be followed up for study purposes at any further visits (i.e. has agreed that any data collected prior to the withdrawal of consent can be used in the study final analysis)

Full details of the reason(s) for withdrawal should be recorded on the Case Report Forms (CRFs) if healthcare professional-initiated, otherwise a simple statement reflecting patient preference, the date of the decision and any reasons given will suffice. Patients who withdraw from study treatment, but continue with on-going follow-up and data collection should be followed-up in accordance with the protocol.

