We will additionally verify the status of 132 (twice as many) test negatives to obtain estimates of the sensitivity and specificity of the test (computed adjusting for the sampling fraction of test negatives). We would expect that these would include 3 found positive for dysplasia and 129 without dysplasia, which will provide over 90% power to show the diagnostic odds ratio is significantly (P<0.05) different from one. A specificity of 95% will be estimated with a confidence interval of less than 4% points.

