11.3. Statistical Analysis for Test Accuracy

Analysis for the primary outcome will estimate positive and negative predictive values of methylation as the proportion of those methylation positive at the initial colonoscopy that are detected with CAN at the reference colonoscopy, and the proportion methylation negative that are free of CAN at the reference colonoscopy, respectively. The diagnostic value of the test will also be summarised as a diagnostic odds ratio, and values of sensitivity and specificity will be computed from predictive values utilising knowledge of the prevalence of CAN and the sampling fraction in those methylation negative. All estimates will be presented with 95% confidence intervals.

The baseline characteristics of the patients enrolled in the study will be examined and planned subgroup analyses will be undertaken using generalised estimating equation logistic regression models. Subgroup analyses are limited by statistical power and will be interpreted with appropriate caution.

Analyses for the primary outcome comparing results of the reference colonoscopy with methylation testing will only be made at a patient level. Although multiple samples are available from each, they cannot be matched at a lesion level as they are based on separate colonoscopic examinations. A patient will be defined as methylation positive if they are positive for any sample, likewise they will be defined as CAN positive if they are histology positive for any sample.

Analysis of the secondary objective of the diagnostic value of methylation will compare results from the same examination, and both lesion and patient level analyses will be possible. Lesion based analyses will take into account repeated samples from individuals using robust standard errors and hierarchical model structures.

We will also investigate the correlation of methylation in biopsies with methylation of proteins detected in serum and of proteins detected in faecal samples.

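### Random selection protects only the invitation to the repeat colonoscopy, so the assurance against partial verification bias is too strong and the stated adjustment leaves out unverified test positives

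*Protocol*

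**What the plan says.** **The assurance.** Sections 6.5 and 10.1 justify verifying only a sample of methylation-negative patients: chosen at random, "it should be representative of all test negatives, and the results not suspect to partial verification bias".

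**Who reaches the reference standard.** In 6.4, histology-negative test positives "will be identified by the ENDCaP-C Study Office and will be invited to undergo early repeat colonoscopy". Twice as many test negatives are randomly selected and "also will be invited to undergo early repeat colonoscopy". Section 3.1 is more definite: "whilst all patients with positive tests for methylation will undergo the reference standard colonoscopy". Section 6.6 lets a patient leave at any time, or be withdrawn if the clinical team judges participation inappropriate. One withdrawal category covers a patient who "has agreed that follow-up data can be collected at standard clinic visits".

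**The numbers.** Section 11.1 bases power on 66 test positives and adds: "We will additionally verify the status of 132 (twice as many) test negatives". Section 11.2 mentions attrition in its heading but gives no rate for the repeat colonoscopy.

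**The estimator.** Section 11.1 adjusts sensitivity and specificity for the sampling proportion in test negatives. Section 11.3 derives them from the predictive values, the prevalence of colitis-associated neoplasia and "the sampling fraction in those methylation negative". Neither names a corresponding quantity for test positives.

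**Safeguards.** Willingness to have the extra colonoscopy is an inclusion criterion (4.2). Methylation results are withheld from patients and clinicians (6.2, 6.4). Completeness of verification is reported to the Steering Committee (9.2.2). Section 6.5 concedes that verification bias cannot be wholly removed, but because of what the histologist knows, not because of non-attendance.

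**The concern.** Partial verification bias concerns who receives the reference standard, not who is offered it. A random draw makes the invited test negatives representative of all test negatives. It cannot do so for those who attend, and it says nothing about test positives, who are not sampled at all. The protocol declares the problem absent while leaving the route by which it would enter unaddressed.

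Two things are at stake:

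- Sensitivity and specificity rest on scaling test negatives up to the cohort. If test positives are not scaled for their own losses, the two groups no longer stand in their true proportion.
- PPV, a primary outcome, is estimated among attending test positives. If attendance is related to undetected dysplasia, PPV moves.

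The base of the sampling fraction is also open. The 2:1 ratio applies to patients selected and invited in 6.4, but to patients verified in 11.1.

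**Working it through.** **1. The plan's own figures (11.1).** Of 1000 patients, 40 have dysplasia found at first histology, which leaves 960. Another 40 have missed dysplasia. At 50% sensitivity that gives 20 true positives and 20 false negatives. At 95% specificity, 5% of 920 gives 46 false positives and 874 true negatives. So there are 66 test positives and 894 test negatives, and PPV = 20/66 = 30.3%. Expected dysplasia among 132 sampled negatives is 132 × 20/894 = 2.95 (plan: 3).

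Power for PPV above 15%, normal approximation, two-sided 0.05, PPV 30%:

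(0.15√66 − 1.96√(0.15×0.85)) / √(0.30×0.70) = (1.219 − 0.700)/0.458 = 1.13, giving 87%.

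This matches the stated 87%, with all 66 verified.

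**2. Attendance unrelated to disease.** The documents give no uptake rate, so I assume a range. Let u be uptake among test positives. Suppose test negatives are weighted from verified patients up to 894 and attending test positives are counted once. Then sensitivity = 20u/(20u+20) and specificity = 874/(874+46u). The power column uses the formula above with PPV = 20/66.

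| u | Verified positives | Sensitivity | Specificity | PPV power |
|---|---|---|---|---|
| 100% | 66 | 50% | 95.0% | 88% |
| 90% | 59 | 47% | 95.5% | 85% |
| 80% | 53 | 44% | 96.0% | 82% |
| 70% | 46 | 41% | 96.4% | 77% |
| 60% | 40 | 38% | 96.9% | 72% |

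**3. The same data by other readings of 11.3, u = 70%.** PPV is 14/46.2 = 30.3%, unchanged, and 1 − NPV (negative predictive value) is 20/894 = 2.24%.

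- With the known test-positive share, 66/960 = 6.875%: sensitivity = (0.303×0.06875)/(0.303×0.06875 + 0.0224×0.93125) = 50%, and specificity is likewise 95%. A true prevalence of 40/960 gives the same result.
- With prevalence estimated from the study by weighting negatives only: (14+20)/(14+32.2+894) = 34/940.2 = 3.6%. Sensitivity is then 14/34 = 41%.
- With negatives weighted by the invited fraction and uptake equal in both groups: 20u/(20u+20u) = 50%. The loss cancels, but only because uptake is equal.

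**4. Attendance related to dysplasia.** Let d be uptake with missed dysplasia and n uptake without. Then PPV = 20d/(20d+46n).

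- d = 60%, n = 80%: 12/(12+36.8) = 24.6%.
- d = 80%, n = 60%: 16/(16+27.6) = 36.7%.

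If uptake depends on dysplasia alone, the diagnostic odds ratio is (20d × 874n)/(46n × 20d) = 19.0, unchanged. Weighting by methylation result rescales all test positives by one factor and so cannot change PPV.

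**5. Bounds without assuming why patients are missing.** At 80% uptake, 53 are verified, about 16 of them with dysplasia, and 13 are unverified. PPV lies between 16/66 = 24% and (16+13)/66 = 44%.

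**The case against.** The strongest reply is that 11.3 does not prescribe a raw cell count. It works through predictive values, which random non-attendance leaves intact, and step 3 shows that this route can return exactly 50% and 95%. A reader might infer from the table that sensitivity and specificity are bound to be biased even when attendance is random. The documents do not support that. What stands is that 11.3 names prevalence without saying where it comes from, names no test-positive share, and so does not exclude the biased version.

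A reader might also infer three different quotas for test negatives, adding the statement in 6.5 that "we will match the numbers of controls recruited at the study level and not within each hospital". That sentence gives no ratio. It says that numbers are balanced across the study rather than by hospital, so that histologists cannot exploit the ratio. The real difference is between invited (6.4) and verified (11.1). Nor does any section say that non-attending test negatives are replaced; this could only be inferred from the 132.

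The withdrawal categories in 6.6 are workable: optional blood and stool samples can be declined while the visit is kept.

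For PPV, the safeguards in 4.2, 6.2 and 6.4 make strongly selective attendance less likely, and the 60% v 80% contrast is assumed. That is fair. But none of them says what happens to unverified patients. Detailed handling may properly sit in an analysis plan not shown here; the explicit assurance and the one-sided adjustment are in the protocol itself.

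**Conclusion.** The point holds in a limited form. The assurance in 6.5 and 10.1 covers the sampling of test negatives and nothing after the invitation. Sections 3.1 and 11.1 assume complete verification that 6.4 and 6.6 do not guarantee. The named adjustment covers only one methylation group, and its base is unsettled.

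The size is conditional. Sensitivity falls to 41%, and specificity rises to 96.4%, at 70% uptake only if test-positive losses are left unweighted while negatives are scaled to 894. PPV moves to 25% or 37% only if uptake is related to dysplasia to the assumed degree. Under random non-attendance PPV is unbiased, although its power drops. The odds ratio is unaffected by random losses and by uptake that depends on dysplasia alone. All uptake rates are assumptions.

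This should be corrected before analysis, but it does not undermine the design.

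**What to change.** 1. In 11.1 and 11.3, replace the test-negative sampling fraction with the verified fraction (verified / all histology-negative patients) in each methylation group. Equivalently, combine PPV and NPV with the observed test-positive share. Estimate these fractions within the risk factors already collected where numbers allow; about 20 true positives and 3 verified false negatives will not support much stratification.
2. Put the 2:1 ratio on one base, invited or verified, in both 6.4 and 11.1, and reconcile 3.1 with 6.4.
3. Report uptake by methylation group, and add a sensitivity analysis for unverified patients, such as the bounds in step 5. Weighting by methylation result does not correct disease-related uptake, so this analysis is needed for PPV. Routine histology that 6.6 already allows to be collected could support it, but without the standardised dye spray and fixed window it is a different reference standard.
4. In 6.5 and 10.1, limit the assurance to the sampling of test negatives and acknowledge non-attendance.

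The cost is wording, a short additional analysis and slightly wider confidence intervals from weighting both groups. Recruitment and procedures do not change.

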6.6. Withdrawal of treatment or protocol violation

Patients may withdraw at any time during the study if they choose not to continue, or if their clinical team feel that continued participation in the study is inappropriate.

There are different types of withdrawal:

- The patient would like to withdraw from the study specific tests and procedures, but is willing to be
 followed-up according to the study protocol (i.e. has agreed to attend study specific follow-up visits
 and that follow-up data can be collected)
- The patient does not want to attend study specific follow-up visits, but has agreed to be followedup according to standard practice (i.e. has agreed that follow-up data can be collected at standard clinic visits)
- The patient is not willing to be followed up for study purposes at any further visits (i.e. has agreed that any data collected prior to the withdrawal of consent can be used in the study final analysis)

Full details of the reason(s) for withdrawal should be recorded on the Case Report Forms (CRFs) if healthcare professional-initiated, otherwise a simple statement reflecting patient preference, the date of the decision and any reasons given will suffice. Patients who withdraw from study treatment, but continue with on-going follow-up and data collection should be followed-up in accordance with the protocol.

6.7. Compatibility with other studies

Patients can be in both ENDCaP-C and other non-interventional studies.

If the patient is part of another interventional study, they may still be able to be recruited to ENDCaP-C. Please contact the ENDCaP-C Study Office to discuss these patients' eligibility prior to entry into other studies.

7. SAFETY MONITORING PROCEDURES

The collection and reporting of data on adverse events and serious adverse events will be in accordance with ICH GCP and the Research Governance Framework 2005. It is imperative that all investigators have a thorough understanding of anticipated adverse events and the reporting process of these events.

There are no (serious) adverse events which would be anticipated as a unique consequence of participation in the study. Any study-related serious adverse events (SAEs) which require immediate reporting will be reported on a study-specific SAE form and will follow the procedure/timeframes outlined in this section of the protocol.

7.1. General Definitions

Serious Adverse Events (SAEs)

An SAE is an untoward event which:

- · Results in death
- Immediately threatens the life of participant*
- Results in hospitalisation or a longer than anticipated stay in hospital
- Results in a persistent or significant disability
- Results in any congenital anomaly or birth defect in any pregnancy

*Life-threatening in the definition of a serious adverse event or serious adverse reaction refers to an event in which the subject was at risk of death at the time of the event. It does not refer to an event which hypothetically might have caused death if it were more severe. Important adverse events/reactions that are not immediately life-threatening or do not result in death or hospitalisation, but may jeopardise the subject or may require intervention to prevent one of the other outcomes listed in the definition above, should also be considered serious.

Serious adverse events specific to the ENDCaP-C study include, but are not limited to:

- Bowel injury/perforation
- Post-colonoscopy bleed requiring admission to hospital
- Inpatient admission for exacerbation of chronic colitis

Expected SAEs

The following are SAEs that could be reasonably expected for this group of patients during the course of the study:

- Hospitalisations for routine treatment or monitoring of the studied indication, not associated with any deterioration in condition
- Hospitalisations for treatment, which was elective or pre-planned, for a pre-existing condition that
 is unrelated to the indication under study, and did not worsen
- Admission to a hospital or other institution for general care, not associated with any deterioration in condition
- Treatment on an emergency, outpatient basis for an event not fulfilling any of the definitions of serious given above and not resulting in hospital admission
- Hospitalisations for planned surgery following non-response to UC treatment

For the purposes of this study these expected SAEs do **NOT** require reporting on an SAE form. These events should continue to be recorded in the source data according to local practice and be included on the routine follow-up CRFs.

Disease related morbidity and routine treatment or monitoring of a pre-existing condition that has not worsened will **NOT** be considered as SAEs and should **NOT** be reported to the Study Office.

